4.7.3 SVC

4.7.3.1 Definition of Endpoints

The endpoint is the mean change from baseline in % predicted SVC (or VC) at Week 24.

For this EAP study, the SVC is measured at Screening/Baseline and Week 24 visit with the 3 best trials recorded on the eCRF. The % predicted SVC value will be calculated at each visit for analysis following the calculation algorithm in Appendix 3. For historical control group, the % predicted VC (based on collected SVC or FVC) will be used.

4.7.3.2 Main Analytical Approach

For participants in FAS, the % predicted SVC (or VC) as well as the change from baseline will be summarized descriptively at Baseline and Week 24 by treatment group.

For EAP study treatment groups, an analysis of covariance (ANCOVA) model with change from baseline at Week 24 as the dependent variable, including main effects for treatment group, bulbar onset (Yes/No) and baseline value will be performed. The % predicted SVC change from baseline's least square mean (SE) and 2-sided 95% CI for each treatment group will be provided at Week 24.

For comparison between PS matched (based on the pre-specified caliper width for main analysis) Trehalose group vs. historical control group, a linear mixed effects model will be used, including the % predicted VC change from baseline at Week 24 as the dependent variable, with fixed effects for treatment group, bulbar onset (yes/no), and baseline value, with propensity score matched ID as the random effect. At Week 24, the % predicted vital capacity change from baseline's least square mean (SE) and 2-sided 95% CI for PS matched Trehalose and historical control groups will be presented. The difference (SE) and 95% CI, p-value for PS matched Trehalose vs. historical control will be summarized.

4.7.3.3 Sensitivity Analyses

To assess the treatment effect in %predicted VC, the following sensitivity analyses will be performed using similar approaches as described in the main analysis:

- % Predicted VC comparison between PS matched (based on other caliper widths) Trehalose group and historical control group, including PS matched ID as random effect using the linear mixed effect model
- % Predicted VC comparison between PS stratification-based Trehalose group and historical control group, including PS stratification-built strata as fixed effect using ANCOVA model

4.7.3.4 Supplementary Analyses

The following analyses will also be performed for the participants in PPS, using the same approaches as described above.

- % Predicted SVC summary for EAP study by treatment cohort and overall
- % Predicted VC comparison between PS matched (based on the pre-specified caliper width for main analysis) Trehalose and historical control groups
- Predicted VC comparison between PS stratification-based Trehalose group and historical control group

4.7.4 ALSAQ-40

The ALSAQ-40 consists of forty questions that are specifically used to measure the subjective well-being of participants with ALS and motor neuron disease. It evaluates 5 dimensions of health status that are affected by the disease: physical mobility (10 items), activities of daily living and independence (10 items), eating and drinking (3 items), communication (7 items), and emotional reactions (10 items). Refer to Table 5 for dimensions and corresponding items from ALSAQ-40 questionnaire.

For each question, participants are asked to select one of the five options according to the frequency of each event experienced during the last two weeks, and a score is assigned for each option: 0=never, 1=rarely, 2=sometimes, 3=often, 4=always or cannot do at all.

The score of items for each dimension will be summed up, then transformed on a scale of 0 to 100 using the equation: (score of each dimension/4) x 100, with 0 indicating perfect health and 100 indicating worst possible health status. The ALSAQ-40 total score represented as symptom index will be calculated as (sum of scores of the 40 individual items)/4 x 100. The specific dimensions and symptom index scoring algorithms are shown in Table 5.

Table 5 ALSAQ-40 Dimensions and Symptom Index Scoring Algorithms

Dimension Scale	Number of Items	Item (Question)	Scoring Algorithm
Physical Mobility	10	Q1 - Q10	If two or fewer of the 10 items are missing, then scale score = 25 x mean of (all available items raw score); otherwise, set the scale score as missing.
Activities of Daily Living/Independence	10	Q11 - Q20	If two or fewer of the 10 items are missing, then scale score = 25 x mean of (all available items raw score); otherwise, set the scale score as missing.
Eating and Drinking	3	Q21 - Q23	If none of the 3 items is missing, then scale score = 25 x mean of (all available items raw score); otherwise, set the scale score as missing.
Communication	7	Q24 - Q30	If one or fewer of the 7 items is missing, then scale score = 25 x mean of (all available items raw score); otherwise, set the scale score as missing.
Emotional Reactions	10	Q31 - Q40	If two or fewer of the 10 items are missing, then scale score = 25 x mean of (all available items raw score); otherwise, set the scale score as missing.
Symptom Index (for total score)	40	Q1- Q40	If eight or fewer of the 40 items are missing, then scale score = 25 x mean of (all available items raw score); otherwise, set the scale score as missing.

For ALSAQ symptom index and each subscale, the score and change from baseline will be summarized descriptively at Baseline and Week 24 for EAP study treatment groups for FAS. At week 24, the least square mean (SE) and 2-sided 95% CI for each treatment group will be provided using the analysis of covariance (ANCOVA) model with change from baseline at Week 24 as the dependent variable, including main effects for treatment group, bulbar onset (Yes/No) and baseline value as covariate.

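### The SAP text for ALSAQ-40 scoring divides item sums by 4, giving scores up to 1000 per dimension and 4000 for the index, and contradicts Table 5

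*SAP*

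**What the plan says.** SAP Section 4.7.4 defines the item responses as "0=never, 1=rarely, 2=sometimes, 3=often, 4=always or cannot do at all". It lists the dimensions as "physical mobility (10 items), activities of daily living and independence (10 items), eating and drinking (3 items), communication (7 items), and emotional reactions (10 items"), which makes 40 items in all.

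The running text then gives two formulas:

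- **Dimensions.** "The score of items for each dimension will be summed up, then transformed on a scale of 0 to 100", by the equation ("score of each dimension/4) x 100, with 0 indicating perfect health and 100 indicating worst possible health status".
- **Symptom index.** "The ALSAQ-40 total score represented as symptom index will be calculated as (sum of scores of the 40 individual items)/4 x 100".

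The next sentence refers the reader to Table 5 for the specific algorithms. For every scale, Table 5 sets "scale score = 25 x mean of (all available items raw score"), subject to a limit on missing items: two for each 10-item dimension, none for Eating and Drinking, one for Communication and eight for the symptom index.

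The resulting scores are used in the baseline summaries (Section 4.4.2). In Section 4.7.4 they are used in the Baseline and Week 24 summaries, the changes from baseline, and the ANCOVA least squares means with standard errors and confidence intervals.

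**The concern.** A sum of k items, each scored 0 to 4, runs from 0 to 4k. To put it on a 0–100 scale one divides by 4k. The text divides by 4 whatever the number of items, so its dimension formula cannot give the range stated in the same sentence. It also disagrees with Table 5 a few lines below.

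A programmer who follows the sentences would produce scores outside the instrument's range, inflated by a different factor in each dimension. Dimension scores could then not be compared with one another, or with any result reported on 0–100. Two programmers working independently, one from the text and one from the table, would not agree. Section 1 says the results might be included in a regulatory submission, and the SAP is where a reader would look to learn how a reported score was derived.

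**Working it through.** **Inputs, all from SAP Section 4.7.4.** Item range 0 to 4. Number of items k: Physical Mobility 10, Activities of Daily Living/Independence 10, Eating and Drinking 3, Communication 7, Emotional Reactions 10, symptom index 40. The stated upper end of the dimension scale is 100.

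**Formulas.** The largest possible item sum is 4k.

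- Text: score = (sum/4) × 100, so the maximum is (4k/4) × 100 = 100k.
- Table 5: score = 25 × mean, so the maximum is 25 × 4 = 100 for every k.

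**Does either rule reproduce the plan's stated maximum of 100?**

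| Scale | k | Largest sum | Text maximum | Table 5 maximum | Ratio |
|---|---|---|---|---|---|
| Physical Mobility | 10 | 40 | 1000 | 100 | 10 |
| Activities of Daily Living/Independence | 10 | 40 | 1000 | 100 | 10 |
| Eating and Drinking | 3 | 12 | 300 | 100 | 3 |
| Communication | 7 | 28 | 700 | 100 | 7 |
| Emotional Reactions | 10 | 40 | 1000 | 100 | 10 |
| Symptom index | 40 | 160 | 4000 | 100 | 40 |

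Table 5 reproduces 100; the text does not. The problem is not confined to extreme patients, because any sum above 4 already exceeds 100 under the text formula. That covers 36 of the 41 possible sums for a 10-item dimension, 24 of 29 for Communication, 8 of 13 for Eating and Drinking and 156 of 161 for the index. A participant who scores 2 on all 40 items has an index of (80/4) × 100 = 2000 by the text and 25 × 2 = 50 by Table 5.

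**Can the text be read another way?** If the score being divided were the item mean, then mean/4 × 100 = 25 × mean, which is Table 5. The wording rules this out: the dimension items are explicitly summed, and the index formula names the sum of the 40 items.

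**Missing items.** The text has no rule for them. Take a participant who scores 2 on every answered item of a 10-item dimension, with 10 answered at Baseline and 8 at Week 24. Table 5 allows this and gives 25 × 2 = 50 at both visits, a change of 0. Summing the answered items under the text formula gives (20/4) × 100 = 500 and then (16/4) × 100 = 400. That is a change of −100, an apparent improvement produced only by the two skipped items. Here the rules differ by more than a constant.

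**Check of the correction.** 100 × sum/(4 × number answered) equals 25 × mean of answered items algebraically. With complete items the two were confirmed equal at every possible sum of each scale.

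**The case against.** The strongest reply is that the section already contains the working rule. The sentence straight after the index formula refers to Table 5 for the algorithms. Table 5 covers all five dimensions and the index, is arithmetically correct, and is the only place with missing-item limits. On this view the prose is a faulty summary of a sound specification. A programmer would use the table, and scores of 300 to 4000 on a 0–100 instrument would be noticed.

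The consequences would also be limited. ALSAQ-40 is exploratory (Section 1.1), there is no formal hypothesis testing (Section 2), and the historical-control comparisons cover only survival, ALSFRS-R and % predicted SVC (Section 4.7). For complete questionnaires the factor is constant within a scale, so means, standard errors and confidence limits rescale together and no direction or relative precision changes.

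Two refinements are also fair. The 1000 applies only to the three 10-item dimensions. The explicit 0–100 statement is attached to the dimension scores; for the index, that range follows from Table 5.

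These points stand as limits on the harm. They do not make the text right. The reference presents Table 5 as the detail of the formulas just given, not as overriding them, and no order of precedence is stated. The dimension sentence contradicts its own range even without the table. The constant-factor argument also fails once items are missing.

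**Conclusion.** The concern holds. Both formulas in the text of SAP Section 4.7.4 are wrong as written and conflict with Table 5. With complete questionnaires they overstate scores by a factor of 10 for three dimensions, 7 for Communication, 3 for Eating and Drinking and 40 for the symptom index. With missing items the discrepancy also depends on how many items were answered at each visit. This rests only on the SAP's own item coding, item counts and stated formulas.

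The actual effect on results depends on which rule was programmed, which the documents do not show. If Table 5 was followed, the scores are valid and only the text needs correcting. If the sentences were followed, every ALSAQ-40 summary, change from baseline and ANCOVA estimate is off the intended scale. Given the correct table and the exploratory role of the endpoint, this is something that should be corrected, not a threat to the study's main conclusions.

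**What to change.** Preferably delete both formulas from the text of Section 4.7.4 and let Table 5 stand as the only scoring specification. If a formula is wanted in the prose, use for the dimensions and the index alike:

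100 × (sum of answered item scores) / (4 × number of items answered),

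which is 25 times the mean of the answered items, applied only when the missing-item limits in Table 5 are met and otherwise set to missing. State explicitly that Table 5 governs.

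The sponsor should also confirm that the analysis programs follow Table 5. A range check that every dimension and index score lies between 0 and 100 would show this at once.

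The cost is two sentences in the SAP and a quick check of the programs. Design, data collection and the intended analysis do not change.

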4.8 Other Analyses

4.8.1 Biomarker Analyses

A descriptive analysis of change in NfL levels will be performed at Baseline and Week 24 for FAS by EAP study treatment groups.

In addition, the NfL levels will be performed using a general linear mixed effects model to compare the rate of decrease (ie, slope) of NfL levels over the 24-week treatment period for FAS. The model will fit a random intercept for each participant and will include fixed effects for treatment group, bulbar onset, visit, and treatment by visit interaction. An unstructured covariance structure will be used to model the within-participant errors. Visit will be expressed in months (using actual study days / 30.4375) as a continuous variable including the baseline visit and all post-baseline visits. Missing values will not be imputed.

Estimates of the slope will be presented by treatment group along with corresponding 95% CIs.

4.9 Safety Analyses

Safety data that will be summarized includes drug exposure, adverse events, clinical laboratory assessments, vital signs, physical and neurologic examinations, C-SSRS assessments. All safety analyses will be based on the FAS and will be summarized by EAP study treatment cohort and overall unless otherwise stated. All data will be provided in the participant data listings.

4.9.1 Extent of Exposure

A summary on the participants' study drug dose modification types (dose initiation, drug interrupted, drug withdrawn) along with primary reasons for dosage change during the study will be provided with number and percentage of participants, and number of events by treatment cohort and overall for FAS.

The following study drug dose exposure variables will be derived and summarized descriptively by treatment cohorts and overall, for FAS and PPS, respectively.

- Number of infusions administered as continuous variable and by categories (1-5, 6-10, 11-15, 16-20, 21-25).
- Number of participants with any treatment infusion interruption, and number of infusion interruptions
- Treatment duration (weeks): defined as (date of last administration – date of first administration + 7) / 7.
- Total volume prescribed (mL): defined as sum of all volume prescribed for the treatment duration, including the missed scheduled infusion visits if any before participants' last infusion. For the missed infusion visits without volume prescribed collected in eCRF, the volume prescribed will be imputed using the last available volume prescribed carried forward from the prior visit.

- Total volume infused (mL): defined as sum of all volume infused for the treatment duration.
- Prescribed dose intensity (mL/week): defined as Total volume prescribed (mL) / Treatment duration (weeks).
- Actual dose intensity (mL/week): defined as Total volume infused (mL) / Treatment duration (weeks).
- Relative dose intensity (%): defined as 100 x (Actual dose intensity / Prescribed dose intensity)
The relative dose intensity (%) will be summarized as continuous variable and presented categorically (< 85%, 85% to 125%, > 125%).

In addition, the same study drug exposure analyses above will be performed for participants with TEAEs related to study drug. Only the infusion data prior to the onset of study drug related TEAEs will be included. Treatment duration (weeks) is defined as (date of last administration prior to the onset of TEAE related to study drug - date of first administration + 7)/7, other exposure variables will be calculated within this treatment duration period.

4.9.2 Adverse Events

Participants will be monitored for adverse events from the time they sign consent for the EAP until completion of their participation as defined in the schedule of assessments.

Severity of AEs

Severity of AEs will be graded as Mild, Moderate, Severe. Missing grades will not be imputed, the AEs with missing grade will be summarized into the category of 'Not Reported' in the tabulation summary.

Relationship of AEs to Study Drug

The relationship of AE to study drug will be determined by Investigator. The relatedness categories include Related and Not Related.

TEAEs

AEs with the date of onset or worsening on or after the date of the first dose of study drug administration will be considered treatment emergent.

TEAEs Summary

AEs with onset after informed consent obtained but before the first dose of study drug will be collected but excluded from adverse event tabulations and presented in listing, only TEAEs are included in the summary by treatment cohort and overall for FAS. The number and percentage of participants with TEAEs will be presented for the summaries as described in **Table 6**. For table of overall summary, the number of events will also be provided.

Table 6 TEAE Summaries

Endpoint	Description
Overall summary	
 • TEAE • TEAE related to study drug • Serious TEAE

Endpoint	Description
	
 • Serious TEAE related study drug • Severe TEAE • Severe TEAE related study drug • TEAE leading to study drug dose reduced • TEAE leading to study drug interrupted • TEAE leading to study drug discontinuation • TEAE leading to early study discontinuation • TEAE leading to death (i.e., outcome is fatal)
TEAE	
 • Overall summary by SOC and PT • Overall summary by SOC, PT, and maximum severity grade • Overall summary by SOC, PT, and time to onset • Overall summary by PT
Most frequently-occurring ($\geq 5\%$) TEAE related to study drug	
 • Overall summary by PT
TEAE related to study drug	
 • Overall summary by SOC and PT • Overall summary by SOC, PT, and maximum severity grade • Overall summary by SOC, PT, and time to onset
Most frequently-occurring ($\geq 5\%$) TEAE related to study drug	
 • Overall summary by PT
Serious TEAE	
 • Overall summary by SOC and PT • Overall summary by SOC, PT, and time to onset
Serious TEAE related to study drug	
 • Overall summary by SOC and PT
Severe TEAE	
 • Overall summary by SOC and PT
Severe TEAE related to study drug	
 • Overall summary by SOC and PT
TEAE leading to study drug discontinuation	
 • Overall summary by SOC and PT
TEAE leading to early study discontinuation	
 • Overall summary by SOC and PT
TEAE leading to death	
 • Overall summary by SOC and PT

- Time to onset is defined as the number of days from the date of the first dose of study drug administration to the date of AE start. The time to onset will be categorized as the following intervals: 0 to 12 weeks, 12 to 24 weeks, and > 24 weeks.
- The summary of most frequently-occurring ($\geq 5\%$) TEAE includes the TEAEs experienced by at least 5% participants in the FAS.
- For AE counting at participant level: A participant having the same event (SOC or PT) more than once will be counted only once. When summarizing events by causality and severity by participants, each participant will be counted only once within a SOC or a PT by using the event with the greatest relationship and maximum severity within each classification.

- For TEAE tables by SOC and PT, the AEs will be presented in descending order of total frequency of both SOC and PT within each SOC. If multiple SOCs or PTs have the same frequency, then they will be sorted in alphabetical order. For TEAE tables by PT only, the AEs will be listed in the descending order of total frequency.

AE listings

Individual listings for the following adverse events will be provided:

- Adverse events
- Serious adverse events
- Adverse events leading to early study discontinuation
- Adverse events leading to death

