6.4.5 Follow-up Safety Call

The follow-up safety call will take place 28 +/- 7 days after the participant's last dose of IP. The following visit procedures (also outlined in the SOA) will be performed:

1. Review adverse events
2. Determine vital status

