3. ANALYSIS SETS

3.1 Definition of Analysis Sets

The following analysis sets are defined for this study:

Analysis Set	Definition
Screened Set	All participants who signed the informed consent form.
Full Analysis Set (FAS)	All participants who received at least one dose of Trehalose.
Per-Protocol Set (PPS)	
All participants included in FAS and who satisfy all the criteria below:
 
 - Did not have a major protocol deviation that affected the scientific integrity of the trial. - Received at least 85% and not more than 125% of the prescribed infusion volume up to the point of drug withdrawal/ last infusion. Data after drug withdrawal/ last infusion will not be included. 
The PPS will be finalized prior to the database closure.

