4. STATISTICAL ANALYSIS

4.1 General Considerations

All data collected will be provided in listings, except data collected only for confirmation of study entry criteria and for study administrative purposes. If any participant is found to not have valid documented informed consent, that participant's data will be excluded from all study datasets, summaries, and listings, except as necessary to document the error.

Unless specified otherwise, the tables and listings for participant dispositions will be based on the Screened Set, all other TFLs will be based on FAS. TFLs will present results by treatment group (or cohort), visit and timepoint as applicable. The Trehalose treatment group labels used in analyses are displayed in Table 2. In addition, the historical control groups constructed in Section 4.2 will be included for comparison analysis between combined Trehalose group with historical control groups.

Table 2 Treatment Group Label

Treatment Group Label
Cohort 1 – Trehalose Naive
Cohort 2 – Platform Trial RGE Roll-over
Trehalose Total

All medical history and adverse events will be coded using Medical Dictionary for Regulatory Activities (MedDRA) 23.0; the primary system organ class (SOC) will be used for analyses. The medications will be coded using the World Health Organization (WHO) Drug Dictionary: WHODrug Global B3 September 1, 2020, a few medications not available in this version will be coded using WHODrug Global B3 March 1, 2023.

Except where specified otherwise, all continuous variables will be summarized with descriptive statistics (the number of non-missing values, mean, standard deviation (SD), median, lower quartile (Q1), upper quartile (Q3), minimum and maximum) and all categorical variables will be summarized with frequency counts and percentages in each category, by treatment group.

For conversion of days to years, months, or weeks, the following conversion factors will be used:

- 1 year = 365.25 days
- 1 month = 30.4375 days
- 1 week = 7 days

All analyses will be conducted using SAS version 9.4 or higher.

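### At a constant event rate, the TEAE time-to-onset tables in SAP 4.9.2 would show a sharp drop after Week 24, because the last interval holds about 4 weeks rather than 12 and no person-time is given

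*SAP*

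**What the plan says.** Table 6 of SAP 4.9.2 lists a summary by SOC, PT and time to onset for each of three groups: all TEAEs, related TEAEs and serious TEAEs. The notes below it set the clock and the cut-points: "Time to onset is defined as the number of days from the date of the first dose of study drug administration" to the AE start date, grouped as "0 to 12 weeks, 12 to 24 weeks, and > 24 weeks".

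- **Statistic.** "The number and percentage of participants with TEAEs will be presented for the summaries as described in" Table 6. Event counts are added only for the overall summary table.
- **Population.** "only TEAEs are included in the summary by treatment cohort and overall for FAS". SAP 4.1 sets the default: apart from disposition, "all other TFLs will be based on FAS". SAP 3.1 defines the FAS as "All participants who received at least one dose of Trehalose", however long each person was followed.
- **Counting.** "A participant having the same event (SOC or PT) more than once will be counted only once". The SAP does not say whether this applies within each interval or once over the whole study.
- **Length of observation.** Infusions run for up to 24 weeks, and the Week 24 visit is at Day 168 ± 14 (Protocol, Schedule of Activities). The last AE contact is set in Protocol 6.4.5: "The follow-up safety call will take place 28 +/- 7 days after" the last dose.

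SAP 4.9.2 specifies no number at risk, participant-time or exposure-adjusted rate for any interval. SAP 4.9.1 summarises treatment duration but does not link it to these intervals.

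**The concern.** A reader compares percentages across the columns of a time-to-onset table. That is fair only if the columns cover similar observation time in similar numbers of people. Here the third column covers a few weeks, mostly off drug, beside two columns of 12 weeks on treatment. Participants who die or leave also stay in the denominator, although they can no longer report an event.

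Long-term safety is a stated objective (Protocol 2.0; SAP Table 1), and SAP section 1 says the results might be included in a regulatory submission. These are the only planned tables of incidence by period. As laid out, they would show fewer events after Week 24 even if the rate had not changed, and they could hide a modest late rise.

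**Working it through.** The documents give no figure for these tables, so there is nothing to reproduce. The check asks what the tables would show if the event rate were truly constant.

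**Step 1. Length of the third interval** (24 weeks = Day 168)

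- Nominal: last infusion Day 168, call Day 168 + 28 = 196. Length 28 days, or 4 weeks.
- Shortest: last infusion Day 154, call Day 154 + 21 = 175. Length 7 days, or 1 week.
- Longest: last infusion Day 182, call Day 182 + 35 = 217. Length 49 days, or 7 weeks.

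**Step 2. Constant rate, no dropout**

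Assume a 12-week risk of 10%. The hazard is λ = −ln(1 − 0.10)/12 = 0.00878 per week, and the risk over L weeks is 1 − exp(−λL).

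- 12 weeks: 10.0%, in each of the first two intervals.
- 4 weeks: 1 − exp(−0.0351) = 3.5%, or 0.35 of the first interval.
- 7 weeks: 1 − exp(−0.0615) = 6.0%, or 0.60.
- 1 week: 0.9%, or 0.09.

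If each participant counts once over the whole study, the figures are 10.0%, then 0.90 × 10.0 = 9.0%, then 0.81 × 3.45 = 2.8%.

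**Step 3. Add early stopping**

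The documents give no attrition rate. Assumptions: 0 to 40% stop by Week 24 with exponential stopping times; half of the stops are deaths with no further follow-up; the rest are observed for 4 weeks after the last dose. The stopping results come from simulating 400,000 participants with a 10% 12-week risk and a 4-week tail. Entries are percentages of the FAS in the three intervals.

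| Stop by Week 24 | Counted once per interval | 2nd/1st | 3rd/1st | Counted at first onset only | 2nd/1st | 3rd/1st |
|---|---|---|---|---|---|---|
| 0% | 10.0 / 10.0 / 3.5 | 1.00 | 0.35 | 10.0 / 9.0 / 2.8 | 0.90 | 0.28 |
| 20% | 9.6 / 8.6 / 2.8 | 0.90 | 0.29 | 9.6 / 7.8 / 2.3 | 0.81 | 0.24 |
| 40% | 9.2 / 7.1 / 2.1 | 0.78 | 0.23 | 9.2 / 6.4 / 1.7 | 0.70 | 0.18 |

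Sensitivity to tail length, counted once per interval: with a 7-week tail the third/first ratio is 0.60, 0.50 and 0.40 at 0%, 20% and 40% stopping. With a 3-week tail and 20% stopping it is 0.22.

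Sensitivity to event frequency: with a 50% 12-week risk and 20% stopping, the figures are 48 / 43 / 17 (third/first 0.35) counted per interval, and 48 / 22 / 4 (0.09) counted at first onset only. For common events the counting rule therefore matters a great deal.

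**Step 4. What corrects it**

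*Number at risk alone does not.* With no dropout, the number at risk equals the FAS and the table still reads 10.0 / 10.0 / 3.5. With 20% stopping, 100%, 91% and 82% are under observation at the interval starts. The third figure then rises only from 2.8% to 2.8/0.82 = 3.4%.

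*Person-time does.* With 70 participants and 20% stopping, mean observation per participant is 11.53, 10.36 and 3.23 weeks. That gives 70 × 11.53 = 807, 725 and 226 participant-weeks. Expected events are 0.00878 × 807 = 7.1, 6.4 and 2.0, which is 0.88 per 100 participant-weeks in every interval.

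*The denominator must match the count.* Take a 30% 12-week risk with no dropout, so λ = 0.0297 and the 4-week risk is 11.2%. First onsets are 30.0%, 0.7 × 30.0 = 21.0% and 0.49 × 11.2 = 5.5%. Divided by all observed time (12, 12 and 4 weeks), they read 2.50, 1.75 and 1.37 per 100 participant-weeks, a spurious 45% fall. Divided by event-free time, they return 2.97 in each interval.

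**The case against.** The SAP never states the denominator for these tables. It follows from the FAS default and the FAS definition, but the Data Presentation Plan holds the shells and could specify something else. This stands as a limit: the point is about what the SAP text leads to.

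The analysis is descriptive and single-arm, no test or decision rule uses these tables, and the third column is visibly the one beyond the treatment period. All true. That limits the harm to how the safety pattern is read, but the label does not tell a reader that the column holds about 4 weeks rather than 12.

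The attrition figures are assumed. Cohort 1 needs a life expectancy of at least 6 months, and Cohort 2 has completed the parent trial, so retention could be good. The main effect survives this, since it is present at 0% stopping.

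A reader might infer two stronger things. One is a steep artificial fall across all three intervals. The figures do not support it in general: the first two intervals are equal in length, and counted per interval the fall between them is 0 to 22% for 0 to 40% stopping. It becomes large only if first onsets alone are counted and the event is common. The other is that these tables are the SAP's only information on event timing. They are not: SAP 4.9.1 also summarises exposure before the onset of related TEAEs, and the AE data are listed.

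**Conclusion.** The point holds in a bounded form. At a constant rate and a 10% 12-week risk, the third interval reads about one quarter to one third of the first with a 4-week tail (0.35 with no dropout, 0.23 with 40% stopping), and about half (0.40 to 0.60) with a 7-week tail, counting once per interval. Interval length does most of this; the shrinking risk set adds to it. The size between the first two intervals cannot be fixed from the documents, because neither attrition nor the scope of once-only counting is given. The result rests on the FAS denominator being applied as the SAP reads and on a constant hazard as the reference case. No inferential result changes. It is a worthwhile and inexpensive correction to the reporting of a stated safety objective.

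**What to change.** In the three time-to-onset tables of SAP 4.9.2 and their shells:

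1. For each interval, add the number of participants under AE observation at its start, the participant-weeks at risk and the incidence per 100 participant-weeks. Do not rely on an at-risk percentage alone, because it does not correct for unequal interval length.
2. State whether once-only counting applies within each interval or over the whole study.
3. Match the denominator to that rule: event-free time if only first onsets are counted, observed time if events are counted.
4. Footnote the interval beyond 24 weeks as shorter than the others and mainly post-treatment follow-up, noting that the last infusion may fall after Day 168 within the visit window.

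The SAP already uses first-dose, last-dose and study completion or discontinuation dates (SAP 4.3 and 4.9.1), so little new derivation is needed. The cost is SAP and shell wording, minor programming and slightly busier tables.
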